4.3 Unscheduled Visits

Due to the complexity of the study, no unscheduled visits will be permitted.

4.4 Subject Completion/Withdrawal

Subjects may withdraw from the study at any time without prejudice to their care. They may also be discontinued from the study at the discretion of the Investigator for lack of adherence to study treatment or visit schedules, or AEs. The Investigator or the Sponsor may also withdraw subjects who violate the study plan, or to protect the subject for reasons of safety or for administrative reasons. It will be documented whether or not each subject completes the clinical study. If the Investigator becomes aware of any serious, related adverse events after the subject completes or withdraws from the study, they will be recorded in the source documents and on the CRF.

5 STUDY EVALUATIONS AND MEASUREMENTS

5.1.1 Medical Record Review

Variables that may be abstracted from the medical chart (paper or electronic):

- Date of birth
- Sex
- CF genotype
- Medications
- History of liver disease, CF related diabetes, GI disease or abdominal surgery

5.1.2 Laboratory Evaluations

Plasma Total Fatty Acids: A total plasma fatty acid panel will be assessed (ARUP Laboratories) to measure change in status of 22 fatty acids.

Fat Soluble Vitamins: Serum vitamin A and vitamin E assessed at Craft Technologies Laboratories. Serum vitamin D determined using Liquid Chromatography-Tandem Mass Spectrometry (CHOP). As a measure of vitamin K status, % undercarboxylated osteocalcin ([name] Lab, Yale University) will be assessed.

Serum Bile Acids: Total serum bile acids and 14 bile acid concentrations will be assessed by liquid chromatography tandem mass spectrometry (ARUP Laboratories)

Serum Calprotectin: Serum calprotectin will be obtained as a marker of lung and gut inflammation^{22,23} using a Buhlmann MRP8/14 ELISA kit (Alpco, Salem, NH)).

Safety Assessment: As part of safety assessment, a comprehensive metabolic panel including the ALT and AST liver enzymes, complete blood count and serum pre-albumin will be assessed (CHOP Clinical Laboratory).

5.1.3 Study Assessments

Sleeping Energy Expenditure: The primary outcome for the assessment of energy expenditure is sleeping energy expenditure (SEE). Using indirect calorimetry, SEE and respiratory quotient will be assessed using a computerized metabolic cart Vmax ENCORE at each protocol visit while the child is asleep. SEE will be assessed in the morning if possible and careful note of previous feeding of the child, including the time of day, amount of food, and feeding interval prior to test. SEE is compared to predicted values derived from the World Health Organization that adjust for age, sex and weight²⁶ and Schofield equations that adjust for age, sex, weight and length²⁷. SEE as kcal/d will also be assessed by adjusting for both fat free mass (FFM) and fat mass (FM) obtained from skinfold measurements. Anthropometric Assessment: The outcomes for weight gain, growth and nutritional status will be length, weight, BMI, and head circumference Z scores. Measures of body composition will also be conducted to determine relative muscle and fat stores. All anthropometric techniques will follow those described by Lohman et al^{28} . Weight (0.1 kg) will be measured on a digital electronic scale (Seca, Munich, Germany), length (0.1 cm) on an infantometer, (Holtain, Crymych, UK), and head circumference (0.1 cm) using an insertion tape. Skinfold thickness will be measured (0.1 mm) at the triceps, biceps, subscapular, and supra-iliac sites with a skinfold caliper (Holtain, Crymych, UK) to assess subcutaneous fat stores. Mid upper arm circumference measured with a non-stretchable fiberglass tape (0.1 cm) (McCoy, Maryland Heights, MO). All measurements will be used to generate age-sex-specific Z scores for length, weight, BMI, head circumference, arm circumference, triceps and subscapular skinfolds using WHO reference data^{29,30}. Z scores for growth velocity will also be calculated for the 12 week period using the WHO reference data³¹, and will provide a novel approach to growth response.

Body Composition: Total body composition, total FFM and FM and percent body fat (%FAT) and regional fat deposition, will be assessed by skinfold measurements.

Fecal Elastase I: Pancreatic function will be assessed at both visits by obtaining spot stool samples with fecal elastase 1 to determine the level of pancreatic enzyme activity^{32,33}. Subjects will be provided with the stool collection kit and proper instructions and supplies, and will bring a stool sample back the next day. The stool sample will be stored at -20°C, and analyzed with an enzyme-linked immunosorbent assay kit sent to ARUP Laboratory (Salt Lake City, UT).

Fecal Calprotectin: Spot stool samples will be obtained to determine fecal calprotectin, a marker for gut inflammation (CHOP Laboratories), determined using a QUANTA Lite® ELISA kit.

Dietary Intake: Three day weighed food record will be obtained and calories, macro- and micro-nutrient content averaged over the three days. Families will be trained by staff and provided with scales, spoons and all supplies necessary for the collection of the dietary data. Detailed verbal and written instructions will be provided to ensure that the recording procedures are clearly understood. Also assisting with this will come from the Center for Human Phenomic Science (CHPS) staff and Bionutrition Unit system^{34,35}. Dietary intake of all nutrients will be analyzed using Nutrition Data System for Research software version 2012 developed by the National Coordinating Center (NCC, University of Minnesota. Minneapolis, MN)³⁶.

Health Questionnaire: The questionnaire will be administered by interview by the research staff, and will consist of two sections. The Health History section has general questions about the subject's health history including documentation of medical history, recent hospital admissions and illnesses, medications, and nutrient supplement use. A section describes aspects of environment such household size, insurance for child and whether on

Medicaid. In addition to family contact information (name, address, phone numbers), contact information from two non-household contacts will be collected to maintain contact with the subject in the event that the family cannot be contacted at their primary residence.

Adherence: Questionnaire at the 6 and 12 week in person visit regarding adherence to treatment will be administered. Phone calls will be made to all families at the 3 and 9 week time points and at the 12-week in person visit after ivacaftor treatment has begun to assess adherence to treatment, to trouble-shoot any barriers to adherence, and also to collect information on adverse events experienced within the past four weeks. Adherence to treatment with ivacaftor treatment and pancreatic enzyme medication use will be assessed.

Adverse Events Calendar: Families will be asked about all adverse events for their child at the 12 week protocol visit and during the phone calls at 3 and 9 weeks, and rate by intensity (mild, moderate, severe). Serious adverse events will be reported as per various policies in a timely manner to CHOP IRB, and CHPS.

5.2 Safety Evaluation

As part of safety assessment, a comprehensive metabolic panel including the ALT and AST liver enzymes, complete blood count and serum pre-albumin will be assessed (CHOP Clinical Laboratory).

Dosing will likely be interrupted by the CF clinical care team in subjects with ALT or AST of greater than 5 times the upper limit of normal (ULN).

Subjects will be asked about all adverse events at the 6 and 12 week protocol visits and during the phone calls at 3 and 9 weeks, and rate by intensity (mild, moderate, severe). Serious adverse events will be reported as per various policies in a timely manner to CHOP IRB, and CHPS.

6 STATISTICAL CONSIDERATIONS

6.1 Statistical Methods

Analysis will begin with descriptive analyses of the study sample using means, standard deviations, medians, and ranges for continuous variables, and frequency distributions for categorical variables. Descriptive statistics and exploratory graphing such as frequencies, means, standard deviations, box plots, and scatter plots will be used to assess the normality of the data in terms of the presence of skew and/or outliers.

6.1.1 Analysis of Primary & Secondary Aims

Data Analysis: Analysis will begin with descriptive analyses of the study sample using means, standard deviations, medians, and ranges for continuous variables, and frequency distributions for categorical variables. Descriptive statistics and exploratory graphing such as frequencies, means, standard deviations, box plots, and scatter plots will be used to assess the normality of the data in terms of the presence of skew and/or outliers. Primary Aims: The goals of the primary aims of this study are to determine whether ivacaftor treatment improves SEE and BMI Z score. Secondary Aims: The goal of the secondary aim is to determine whether ivacaftor improves gut health and function as measured by total plasma fatty acids, fecal elastase and fecal calprotectin (ug/g stool). Analysis of efficacy for the primary and secondary outcomes will be based on change from baseline (before treatment) in SEE% predicted (Schofield), BMI Z scores, total plasma fatty acids, fecal elastase continuous

outcomes will initially be compared using paired-t-tests if continuous variables are normally distributed and nonparametric tests (Wilcoxon sign rank) if they are not. Subsequently, mixed effects longitudinal models will be performed to assess change over all three time points (baseline, 6 and 12 weeks), adjusting for potential covariates such as age, sex, and adherence to treatment. Chi-squared tests will be used for comparison of categorical variables before and after ivacaftor treatment. Using similar methods, exploratory analyses will examine improvement in dietary intake of calories and fat, in growth status (weight, length, and head circumference Z scores) and growth velocity (both absolute and Z scores), serum fat soluble vitamins, bile acids, and calprotectin.

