Ivacaftor has shown similar benefit in younger children and has been approved for use in children 6 months and older.. Ivacaftor was found to be safe and effective in 33 children in the KIWI study completed 24 weeks of treatment in the KIWI study, with significant reductions in sweat chloride concentration, and an average increase in weight Z score of 0.2 ± 0.3 and BMI z score of 0.4 ± 0.4^6 . Some exocrine pancreatic function restoration was demonstrated in these young children, as Davies et al.⁶ noted an increase in fecal elastase concentrations in a small sample of children after 24 weeks ivacaftor treatment. Prior to treatment, 93% were PI with fecal elastase concentrations of <50 µg/g, and after treatment this increased 100 µg/g on average. Furthermore, in the KLIMB study, a long-term follow-up to the KIWI study, the increased fecal elastase concentrations were sustained with mean increase of 129 µg/g after 84 weeks of treatment¹⁴. These results suggest that exocrine pancreatic function early in life may be partially restored with ivacaftor^{6,15}.

In a recent open-label Phase 3 trial (the ARRIVAL study)^{16,17} in 18 children ages 1 to 2 years of age with CFTR gating mutations (G551D, G178R, S549N, S549R, G551S,

G1244E, S1251N, S1255P, G1439D, or R117H) who completed 24-weeks of treatment, ivacaftor was safe and effective in significantly reducing sweat chloride concentrations from 104.1 to 31.5 mmol/L, and improving (restoring) pancreatic function as indicated by increasing fecal elastase from 182 to 357 ug/g stool. Ivacaftor's impact on growth status or velocity for weight and BMI in these young children was not reported. Changes in energy expenditure with ivacaftor treatment in these young children has also not yet been explored. This current application will directly ddress gaps in knowledge related to the important non-pulmonary outcomes that are clinically very important in very young children.

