2.3 Exploratory Aims

- 1) To determine the impact of ivacaftor treatment over 12 weeks compared to baseline in:
 - a) Dietary intake of calories and percent calories from fat
 - b) Growth status for length, weight, head circumference and growth velocity
 - c) Serum fat soluble vitamins A, D, E and K, bile acids, and calprotectin

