3.2.2 Total Number of Study Sites/Total Number of Subjects Projected

The study will be conducted at one investigative site in the United States.

Recruitment will stop when 18 subjects are enrolled. It is expected that 18 subjects will be enrolled to produce 16 evaluable subjects.

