6.2 Sample Size and Power

Sample Size and Power: This is a longitudinal study of the effects of ivacaftor treatment on outcomes before and after 12-week treatment. The sample size of 16 subjects to complete the study has been determined as adequate to have the power to test the primary outcomes of decrease in SEE percent predicted value (7% change), an increase in BMI Z score of 0.3, and secondary outcomes of measures of gut health and function; an increase in plasma total fatty acids from 8.5 to 10.5 mmol/L, an increase in fecal elastase of 120 ug/g stool, and a decrease in fecal calprotectin (-30 ug/g stool change). Using STATA, power calculations were generated, with α =0.05, for paired data (n=16) within the same sample (before and after 12 weeks of treatment) using the changes described above for the primary outcomes and secondary outcomes.

Primary outcomes: A sample size of 16 subjects results in 86% power to see a decrease of 7% in **SEE** (i.e. from 115 to 108) with a standard deviation of the change of 9%, using a paired t-test two-sided significance level. We demonstrated a change of similar magnitude in REE in 24 subjects with CF gating mutation after 3-mo treatment with ivacaftor^{7,9}. For growth status, 16 subjects will provide 85% power to detect an increase in **BMI Z score** of 0.3 with a standard deviation of 0.4. In the KIWI study of 2 to 5 year old children with CFTR gating mutation treated with ivacaftor for 24 weeks, a BMIZ score increase of 0.4±0.4 was demonstrated⁶. We showed a BMI Z score increase over 12 weeks of 0.3±0.4 in our recent study of 18 children (5 to 19 years) with 12-week ivacaftor treatment⁷.

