Secondary outcomes: A sample of 16 subjects will provide 80% power to detect an increase in total plasma fatty acids from 8.5 to 10.5 mmol/L with a standard deviation of 2.8%, will provide 88% power to detect an increase in fecal elastase of 120 ug/g stool with a standard deviation of 150 ug/g stool, and will provide 85% power to detect a decrease in fecal calprotectin of 30 ug/g stool with a standard deviation of the change of 40 ug/g stool. We previously demonstrated a 3-month increase in plasma total fatty acids of this magnitude in subjects with CF receiving a fat-based nutritional supplement¹⁹. Davies et al⁶ demonstrated a change of 100 ug/g stool in fecal elastase with 24-week ivacaftor treatment in for 2 to 5 year old children with CFTR gating mutations in the KIWI study, and an even greater increase of 164 ug/g stool fecal elastase was shown in 1 to 2 year old children participating in the ARRIVAL study¹⁶. We have previously demonstrated a 3-month decrease of 30 ug/g stool in fecal calprotectin with ivacaftor treatment in 5 to 61 year old people with CFTR gating mutations⁷. The standard deviations of 9% for SEE, 40 ug/g stool for fecal calprotectin, 150 ug/g stool for fecal elastase and 0.4 for BMI Z score are reasonable estimates of the variability expected in changes for these variables from our experience with 3-12 month changes in these measures in previous longitudinal clinical trials we have conducted for changes in children and adults with CF^{7,18,19,37,38}. In addition, our recent experience with SEE measures in 1 year old healthy children showed a standard deviation of 8% in SEE percent predicted values³⁹ (personal communication).

We plan for up to 12% attrition over the 12 weeks. By enrolling 18 subjects we can account for attrition and also allow for the possibility of greater variability in the SEE, BMI Z scores and gut health and function measures.

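### Section 6.1.1 names only chi-squared tests for before/after categories in the same roughly 16 children; a paired test should be named (minor)

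*Combined protocol and SAP*

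**What the plan says.** Section 6.1.1 of the combined protocol and SAP states: "Chi-squared tests will be used for comparison of categorical variables before and after ivacaftor treatment". The synopsis repeats this under its statistical plan. McNemar's test, a marginal homogeneity test or any other paired test for categories is named nowhere.

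Elsewhere the plan treats the data as paired. For continuous variables, section 6.1.1 says "outcomes will initially be compared using paired-t-tests if continuous variables are normally distributed and nonparametric tests (Wilcoxon sign rank) if they are not". Section 6.2 bases its power figures on a calculation "for paired data (n=16) within the same sample (before and after 12 weeks of treatment" and so on. Section 3.2.2 sets the number: "It is expected that 18 subjects will be enrolled to produce 16 evaluable subjects".

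Section 6.1 foresees "frequency distributions for categorical variables", but no categorical variable or cut-off is listed for a before/after comparison. The listed outcomes are continuous measures. One secondary outcome, for example, is powered for "an increase in fecal elastase of 120 ug/g stool with a standard deviation of 150 ug/g stool", and the first exploratory aim is "Dietary intake of calories and percent calories from fat". The one pancreatic cut-off describes an earlier study: section 1.1 says that before treatment "93% were PI with fecal elastase concentrations of" less than 50 µg/g.

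**The concern.** An ordinary chi-squared test on a visit-by-category table assumes that the two rows come from different people. Here they are the same children, so 16 pairs would be counted as 32 independent observations. This has two consequences.

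- The test uses the wrong variance for the change in proportion, so its actual error rate is not the nominal 5% unless the two values within a child are uncorrelated.
- It sees only the totals at each visit. Which children changed, and in which direction, has no influence on the p-value, although that is what a before/after comparison is about.

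At stake are supporting comparisons only, such as a continuous measure later cut into categories. An analyst who follows the text literally could miss a real shift or report a p-value that does not reflect the changes within children.

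**Working it through.** **1. The plan's own figures.** No power is stated for any categorical comparison. The stated figures can be reproduced as paired calculations for continuous outcomes, with power = Φ(δ/(SD/√16) − 1.96):

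| Outcome (section 6.2) | δ / (SD/4) | Recomputed | Stated |
|---|---|---|---|
| SEE % predicted | 7/2.25 = 3.11 | 87.5% | 86% |
| BMI Z score | 0.3/0.1 = 3.00 | 85.1% | 85% |
| Total fatty acids (SD read as 2.8 mmol/L) | 2/0.7 = 2.86 | 81.5% | 80% |
| Fecal elastase | 120/37.5 = 3.20 | 89.3% | 88% |
| Fecal calprotectin | 30/10 = 3.00 | 85.1% | 85% |

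All are within 2 points. (A noncentral t calculation gives lower values, 76.1% to 84.8%, but that does not bear on this point.) None of these figures rests on the categorical test.

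**2. Why the ordinary test is off.** Let p be the proportion in a category at both visits (no true change) and ρ the within-child correlation. The true variance of the difference in proportions is 2p(1−p)(1−ρ)/n. The ordinary test uses 2p(1−p)/n, so the true variance is (1−ρ) times the assumed one. In large samples the actual size is therefore P(|Z| > 1.96/√(1−ρ)):

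- ρ = 0.3: 1.96/√0.7 = 2.34, size about 1.9%
- ρ = 0.6: 1.96/√0.4 = 3.10, size about 0.2%
- ρ = −0.2: 1.96/√1.2 = 1.79, size about 7.4%

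**3. Exact size at n=16.** The documents give no categorical rates or correlations, so the values of p and ρ are assumptions. All paired 2×2 tables were enumerated, with cell probabilities p² + ρp(1−p) for yes at both visits, p(1−p)(1−ρ) for each type of change, and the rest for no at both. The test rejects if p ≤ 0.05, without continuity correction.

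| p | ρ | Ordinary | McNemar asymptotic | McNemar mid-p | McNemar exact |
|---|---|---|---|---|---|
| 0.5 | −0.2 | 7.5% | 4.2% | 4.2% | 2.3% |
| 0.5 | 0 | 5.2% | 4.3% | 4.0% | 2.0% |
| 0.5 | 0.3 | 2.1% | 5.0% | 3.0% | 1.2% |
| 0.5 | 0.6 | 0.3% | 3.5% | 1.0% | 0.2% |
| 0.8 | −0.2 | 7.7% | 4.8% | 3.3% | 1.4% |
| 0.8 | 0 | 5.3% | 5.0% | 2.7% | 0.9% |
| 0.8 | 0.3 | 2.2% | 4.1% | 1.3% | 0.3% |
| 0.8 | 0.6 | 0.4% | 1.4% | 0.2% | 0.03% |

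A grid of p from 0.20 to 0.80 and ρ from −0.30 to 0.60 in steps of 0.01 has 5,527 feasible points. At ρ ≥ 0 the ordinary test's largest size is 5.8%, at ρ = 0, and by ρ = 0.08 it is below 5% at every p. Its overall maximum, 9.7%, occurs at ρ = −0.30. Over the whole grid, asymptotic McNemar does not exceed about 5.0%.

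**4. Same totals, different children.** Suppose 12/16 before and 7/16 after. The pooled proportion is 19/32, and the ordinary statistic is (5/16)² / [(19/32)(13/32)(2/16)] = 3.24, p = 0.072, whoever changed. McNemar's statistic is (b−c)²/(b+c), where b children left the category and c entered it:

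- b=5, c=0: 25/5 = 5.00, p = 0.025
- b=9, c=4: 25/13 = 1.92, p = 0.166

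**5. Power for an assumed change from 80% to 50%.**

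| ρ | Ordinary | McNemar asymptotic | Mid-p | Exact |
|---|---|---|---|---|
| 0 | 45% | 39% | 37% | 27% |
| 0.3 | 44% | 55% | 47% | 32% |

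**The case against.** **McNemar's test is itself a chi-squared test.** The authors paired every continuous comparison and may well have meant the paired form here. That is fair. A reader might infer that the plan means to ignore the pairing, but the documents show only that the paired form is not named. The gap still matters, because the literal wording allows the ordinary test. The mixed models in section 6.1.1 do not close it, since the categorical sentence names its own test.

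**The sentence has no identified target.** This stands, and it caps the importance of the point. No before/after category or cut-off is listed, and the error rates above rest on assumed proportions and correlations.

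**The ordinary test does not inflate false positives in practice.** This also stands. A reader might take the 9.7% figure as the likely harm, but it needs a correlation of −0.3. Two values from the same child, 12 weeks of treatment apart, would ordinarily be positively correlated, and nothing in the documents suggests otherwise. The realistic problem is a test that is too conservative and blind to who changed.

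**A paired test is not automatically better.** Correct. The exact version is more conservative than the ordinary test at every grid point with correlation zero or above, and it has less power in both examples. Simply asking for McNemar's test is therefore not enough; the version has to be stated.

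**Conclusion.** The point holds as a minor defect of specification. As written, the rule applies an independence test to paired data and is out of line with the paired methods named for continuous outcomes. At n=16 and proportion 0.5, its actual size would be about 2% at a within-child correlation of 0.3 and about 0.3% at 0.6, against a nominal 5%. With zero or positive correlation it does not exceed 5.8% anywhere on the grid examined.

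These sizes assume 16 complete pairs, two-level categories and the stated proportions and correlations, none of which the documents give. That the correlation is positive is a judgement, not a documented fact.

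A reader might go further and infer that the main results or the sample size are compromised. The documents do not support that: the listed primary, secondary and exploratory outcomes are continuous, and every stated power figure belongs to a paired comparison of a continuous outcome.

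**What to change.** In section 6.1.1 and in the synopsis, replace the sentence with:

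> Two-level categories before and after treatment will be compared with McNemar's test (asymptotic form without continuity correction), and categories with more than two levels with a marginal homogeneity test, with the paired difference in proportions and its 95% confidence interval.

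If the sentence stays, list the variables and cut-offs it covers before the data are analysed. If no categorical comparison is planned, delete it in both places.

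The asymptotic form is proposed because it held its size at about 5.0% or less across the grid and had the most power of the three McNemar versions in both examples.

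The cost is one sentence in two places and, where needed, a short list; no new data are required. P-values can move either way. If the within-child correlation is near zero, the paired test has somewhat less power than the ordinary one (39% against 45% for the assumed change from 80% to 50%). At a correlation of 0.3 it has more (55% against 44%).
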